7.1 Study Design

This study is an explorative non-interventional prospective study. Questionnaires will be used as form of intervention. The intervention will take place before and after hormonal stimulation (on the day of pick-up). The aim of this study is to get a view on the prevalence of IBS symptoms in the PCOS and social freezing group.

7.2 Date Range for collected study data

The first inclusions will be done in December 2025 and the last inclusions will be in July 2026. This means that study data will be collected till February 2027.

8 Study Population

8.1 Population of interest

Women with PCOS who are nulliparous and initiate IVF treatment.
Woman who are nulliparous and initiate ovarian stimulation for social freezing.
Both groups will receive PPOS (progestin-primed ovarian stimulation) and will get the freeze-all procedure after pick-up of oocytes.
Patients will be recruited at the fertility clinic of the UZ Brussels.

8.2 Inclusion & exclusion criteria

Inclusion criteria **PCOS** group :

- Diagnosis of PCOS according to the 2004 Rotterdam criteria
- Initiating their first cycle of IVF treatment (PPOS and freeze only protocol)
- Nulliparous
- ≥ 18 years
- Willing to participate in the study
- Understanding Dutch, French or English

Exclusion criteria **PCOS** group :

- Known inflammatory bowel disorder
- Known major intestinal bowel disorder
- Known systemic or auto-immune disorder with implication for the GI system
- History of abdominal surgery (appendectomy and cholecystectomy allowed if >6 months earlier)
- History of gastro-enteritis in the past 6 weeks

Inclusion criteria **social freezing** group:

[figure not shown]
- Initiating their first ovarian stimulation protocol for elective oocyte cryopreservation (PPOS and freeze only protocol)
- Nulliparous
- ≥ 18 years
- Willing to participate in the study
- Understanding Dutch, French or English

Exclusion criteria **social freezing** group:

- Diagnosis of PCOS
- Known inflammatory bowel disorder
- Known major intestinal bowel disorder
- Known systemic or auto-immune disorder with implication for the GI system
- History of abdominal surgery (appendectomy and cholecystectomy allowed if >6 months earlier)
- History of gastro-enteritis in the past 6 weeks

9 Study Assessments and Procedures

9.1 Schedule of Activities

9.2 Detailed Study Assessments

9.2.1 Screening

When a patient visits the fertility clinic and is considered a possible participant for the study, they will be informed about the study. Inclusion and exclusion criteria will be checked. The doctor will go over the informed consent form (ICF) and the patient will get enough time to ask questions. If the patient is eligible and wants to participate in the study, they will sign the ICF.

9.2.2 Visit before fertility treatment

Informed consent will be obtained. The IBS-SSS (IBS Symptom Severity Scale) (appendix 2) and Rome IV Criteria (appendix 1) are used to determine resp. IBS symptom severity and presence. The GSRS (appendix 3) is used to get a more general insight in gastrointestinal symptoms. The Patient Health Questionnaire-9 (PHQ-9) (appendix 5) will be used to determine the depression level of the patient. the Generalized anxiety Disorder 7-item (GAD-7) (appendix 4) examines the anxiety levels. These questionnaires will be available in three languages: Dutch, French and English. The questionnaires will be filled out on paper. In total, it will take about 15 minutes to fill out all the forms.

9.2.3 Visit after fertility treatment

After the fertility treatment (ovarian stimulation) the patient will come to the fertility clinic for pick-up of the oocytes. During this visit the following questionnaires will be filled-out: IBS-SSS (appendix 2) , Rome IV criteria (appendix 1) , GSRS (appendix 3) , PHQ-9 (appendix 5) and the GAD-7 (appendix 4) .

9.3 Assessment types

9.3.1 IBS symptoms

The IBS-SSS (IBS Symptom Severity Scale) (appendix 2) and Rome IV Criteria (appendix 1) are used to determine IBS symptoms. The result of the IBS-SSS is a score of 0 to 500. Each of the five topics is rated from 0 to 100. The topics are number of days with abdominal pain, satisfaction with bowel habits, abdominal pain, bloating/distention and IBS-related quality of life. A 15% change in the score

is considered clinically significant. (29) A score of 75-175 is considered mild, a score of 175 to 300 is considered moderate and a score of >300 is considered severe. (30) The Rome IV Criteria for IBS describe recurrent abdominal pain on average at least 1 day per week in the last 3 months, associated with two or more of the following criteria: associated with a change in the frequency of stool, associated with a change in the form of stool and/or related to defecation. The criteria should be present for the last 3 months and symptoms should be present at least 6 months before the diagnosis is made. (16)

IBS prevalence differs greatly based on if the Rome IV or Rome III criteria are used. The Rome Foundation Global study reported an overall prevalence of 3,8% when the Rome IV criteria are used and an overall prevalence of 10,1% when the Rome III criteria are used. (15) The Rome IV criteria ask for abdominal pain while the Rome III criteria ask for abdominal discomfort (an uncomfortable sensation and not necessary pain). (16) Because of this big difference in prevalence, this study will first ask for abdominal pain (Rome IV criteria) and afterwards ask for abdominal discomfort (Rome III Criteria). This gives us a more complete picture of the IBS symptoms.

9.3.2 *Gastrointestinal symptoms*

The Gastrointestinal Symptom Rating Scale (appendix 3) contains 15 questions divided over five domains: abdominal pain, reflux syndrome, indigestion syndrome, constipation syndrome and diarrhea syndrome. Each question is scored from 1-7 depending on the inconvenience that the person experienced in the previous week. A higher score correlates with more inconvenient symptoms. (31) This questionnaire is used to get a more general overview of gastrointestinal symptoms.

9.3.3 *Depression levels*

The Patient Health Questionnaire-9 (PHQ-9) (appendix 5) will be used to determine the depression level of the patient. The questionnaire contains the nine DSM-V criteria for depression. Each question can be scored from "0" (not at all) to "3" (nearly every day). A score of "0-4" is considered minimal depression, "5-9" is mild depression, "10-14" is moderate depression, "15-19" is moderately severe and "20-27" is severe. (32)

9.3.4 *Anxiety levels*

Thirdly, the Generalized anxiety Disorder 7-item (GAD-7) (appendix 4) examines the anxiety levels. The questionnaire consists of seven questions with each time four response options (not at all = 0, several days = 1, more than half the days = 2 and nearly every day = 3). A total scores determine the severity of anxiety: 0-4 = minimal anxiety, 5-9 = mild anxiety, 10-14 = moderate anxiety and 15 or more = severe anxiety. (33)

9.3.5 *Results on the GAD7 and/or PHQ9 questionnaires*

The GAD and PHQ-9 both are **screening tools** meant for preliminary assessment of anxiety and depression in patients. No specific training is required, and the questionnaires are meant for **self-administration** to the patient. Scoring is only **indicative** of possible underlying disorders, requiring a more comprehensive clinical assessment for confirmation. Therefore, for higher scores, the decision to refer for further specialised assessments relies on the clinical evaluation by the attending physician of the fertility clinic. The scoring will be performed by the student. Scores > 10 for the GAD and PHQ-9 will be communicated to the attending physician.

Both questionnaires will be scored according to the scoring sheet:

Scoring sheet:

GAD-7:

- 5-9: mild symptom severity
- 10-14: moderate
- > 15: severe

PHQ-9:

- 0-4: none
- 5-9: mild depression
- 10-14: moderate depression
- 15-19: moderate to severe depression
- 20-27: severe depression

10 Data Collection and Management

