
Endpoints:
	
The primary endpoint is to explore whether there is a difference between the IBS prevalence before and after ovarian stimulation.
 
The score on the Rome Criteria for IBS before and after ovarian stimulation will be compared.
 
The severity of IBS symptoms before and after the fertility treatment will be compared using the IBS-SSS (IBS- Symptom Severity Scale) questionnaire.
 
The prevalence of gastrointestinal symptoms before and after the fertility treatment will be compared using the GSRS (Gastrointestinal symptom rating scale) questionnaire.
 
The prevalence of anxiety levels before and after the fertility treatment will be compared using the GAD-7 (Generalized Anxiety Disorder 7-item) questionnaire.
 
The depression levels before and after the fertility treatment will be compared using the PHQ-9 (Patient Health Questionnaire 9).
 
The PCOS and social freezing group will each be divided in different subgroups based on the type of stimulation.
 
The IBS prevalence (with the Rome Criteria) and the IBS symptom severity (with the IBS-SSS) will be compared in these subgroups before and after ovarian stimulation.
 
The same will be done based on the number of treatments that were received before this treatment, the duration of -infertility, the number of previous pregnancies, the number of children, the ethnicity, the hormonal profile during COS (continuous ovarian stimulation).
 
The PCOS group will be divided in different subgroups based on the type of PCOS. . The IBS prevalence (with the Rome Criteria) and the IBS symptom severity (with the IBS-SSS) will be compared in these subgroups before and after the fertility treatment.

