6.1.1 Primary research hypotheses

H1.

The prevalence of participants meeting diagnostic criteria for Irritable Bowel Syndrome (IBS), as defined by the ROME III and ROME IV criteria, differs significantly before and after fertility treatment.

H2.

IBS symptom severity, as measured by the IBS Symptom Severity Score (IBS-SSS), changes significantly following fertility treatment compared with baseline.

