APPENDIX 1: ROME IV IBS QUESTIONNAIRE (English version) (Rome Foundation)

Question

40. In the last 3 months, how often did you have pain anywhere in your abdomen?

Answer

- ① Never
- ① Less than one day a month
- ② One day a month
- ③ Two to three days a month
- ④ Once a week
- ⑤ Two to three days a week
- ⑥ Most days
- ⑦ Every day
- ⑧ Multiple times per day or all the time

40b. In the last 3 months, how often did you have discomfort anywhere in your abdomen ?

- ① Never → If you answered "Never" on question 40 and 40b: **Skip question 41**
- ① Less than one day a month
- ② One day a month
- ③ Two to three days a month
- ④ Once a week
- ⑤ Two to three days a week
- ⑥ Most days
- ⑦ Every day
- ⑧ Multiple times per day or all the time

41. How often did this pain in your abdomen happen close in time to a bowel movement -- just before, during, or soon after? (Percent of times with pain)

- ① 0% Never
- ① 10%
- ② 20%
- ③ 30%
- ④ 40%
- ⑤ 50%
- ⑥ 60%
- ⑦ 70%
- ⑧ 80%
- ⑨ 90%
- ⑩ 100% Always

42. How often did your stools become either softer than usual or harder than usual when you had this pain? (Percent of times with pain)

- ① 0% Never
- ① 10%
- ② 20%
- ③ 30%
- ④ 40%
- ⑤ 50%
- ⑥ 60%
- ⑦ 70%
- ⑧ 80%
- ⑨ 90%
- ⑩ 100% Always

43. How often did your stools become either more frequent than usual or less frequent than usual when you had this pain? (Percent of times with pain)

- ① 0% Never
- ① 10%
- ② 20%
- ③ 30%
- ④ 40%
- ⑤ 50%
- ⑥ 60%
- ⑦ 70%
- ⑧ 80%
- ⑨ 90%
- ⑩ 100% Always

48. Has it been 6 months or longer since you started having this pain?

- ① No
- ① Yes

Type 1		Separate hard lumps, like nuts
Type 2		Sausage-shaped but lumpy
Type 3		Like a sausage but with cracks on the surface
Type 4		Like a sausage or snake, smooth and soft
Type 5		Soft blobs with clear-cut edges
Type 6		Fluffy pieces with ragged edges, a mushy stool
Type 7		Watery, no solid pieces

Bowel movements of Type 1 or 2 and also of Type 6 or 7 in the picture above can be considered to be abnormal. Type 1 or 2 means you are constipated, and Type 6 or 7 means you have diarrhea.

64. In the last 3 months, when you had abnormal stools, what were they usually like?

- ① Usually constipation (like Type 1 or 2 in the picture)
- ② Usually diarrhea (like Type 6 or 7)
- ③ Both diarrhea and constipation - that is, more than 1/4 of all the abnormal bowel movements were constipation and more than 1/4 were diarrhea
- ④ Not applicable, because I never or rarely had abnormal bowel movements

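### The primary before/after endpoint, change in Rome IBS prevalence, cannot count symptoms that begin during stimulation, because the criteria require onset at least six months earlier

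*Protocol*

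**What the plan says.** Section 4 (Endpoints) states: "The primary endpoint is to explore whether there is a difference between the IBS prevalence before and after ovarian stimulation". Section 6.1.1 turns this into H1: "The prevalence of participants meeting diagnostic criteria for Irritable Bowel Syndrome (IBS), as defined by the ROME III and ROME IV criteria, differs significantly" between the two time points. Sections 6.1 and 10.5 repeat the aim and place change in IBS-SSS (H2) beside it.

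Section 9.3.1 defines Rome IV IBS as "recurrent abdominal pain on average at least 1 day per week in the last 3 months", together with at least two of three stool-related or defecation-related features, and adds: "The criteria should be present for the last 3 months and symptoms should be present at least 6 months before the diagnosis is made".

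Appendix 1 builds both time rules into the form. The pain item reads "40. In the last 3 months, how often did you have pain anywhere in your abdomen", the discomfort item reads "40b. In the last 3 months, how often did you have discomfort anywhere in your abdomen", and the onset item reads "48. Has it been 6 months or longer since you started having this pain".

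On timing, section 7.1 says: "The intervention will take place before and after hormonal stimulation (on the day of pick-up". Section 9.2.3 confirms that the second set of forms is completed at the pick-up visit. The readable text adds no later visit, no shorter recall and no waiver of item 48.

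**The concern.** Section 5.9 motivates the study by the gastrointestinal side effects of fertility drugs and asks how common such symptoms are during treatment. A primary before/after endpoint for that question should be able to register symptoms that treatment starts. Rome status is a classification of chronic disease, with an onset rule far longer than one stimulation course.

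At stake is how a flat result is read. If many women developed bowel symptoms during stimulation, those symptoms would not add a single Rome IV case. An unchanged prevalence could then be taken as evidence that stimulation does not provoke such symptoms, which the endpoint is not built to show. Recruiting more women, the option left open in section 4, would not help, because the limit lies in the definition and not in the sample size.

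**Working it through.** **Inputs from the protocol.** Recall of items 40 and 40b: 3 months, taken as 91 days (13 weeks). Frequency threshold: 1 pain day per week on average, so 13 pain days in 91. Onset rule: 6 months, taken as 182 days. IBS-SSS recall: 10 days (Appendix 2). GSRS recall: one week (Appendix 3). Sample size: 60 + 60 = 120, given without a power calculation.

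**Assumptions.** The readable text does not give the length of stimulation, D. The range used is 8 to 16 days, with 28 as an extreme. Baseline is taken to be at the start of stimulation; the schedule table in section 9.1 is not readable.

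**Step 1: onset rule, recall window and threshold.** For symptoms starting on day 1 of stimulation:

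| D (days) | Short of the onset rule, 182 − D | Recall before stimulation, (91 − D)/91 | Daily new pain, D/13 days per week |
|---|---|---|---|
| 8 | 174 | 91% | 0.62 |
| 12 | 170 | 87% | 0.92 |
| 13 | 169 | 86% | 1.00 |
| 14 | 168 | 85% | 1.08 |
| 16 | 166 | 82% | 1.23 |
| 28 | 154 | 69% | 2.15 |

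The onset rule blocks new symptoms at every D. The recall alone does not: daily new pain reaches the threshold at 13 days. So the six-month rule is the bar, and the three-month recall only dilutes.

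**Step 2: the other instruments.** For D = 8 to 16, stimulation fills 8/91 = 9% to 16/91 = 18% of the Rome recall. It fills 80% (8/10) to 100% of the IBS-SSS recall and all of the GSRS recall.

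**Step 3: who can still change status.**

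- Upward: a woman with at least six months of pain on 2 to 3 days a month (taken as 2.5) has about 2.5/30.4 × (91 − 12) = 6.5 pain days outside a 12-day course. She needs 13 − 6.5 = 6.5 more during it, which is possible. She converts if the stool and defecation items are also met.
- Downward: a woman exactly at threshold (13 days in 91) with no pain during a 12-day course falls to 13 × 79/91 = 11.3 days, or 0.87 per week. She loses the diagnosis.

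**Step 4: scale.** Section 10.5 plans logistic regression; an exact two-sided McNemar test at an assumed alpha of 0.05 serves here only as a yardstick. Five changes all in one direction give p = 2 × 0.5^5 = 0.0625, and six give 2 × 0.5^6 = 0.031. So at least six are needed: 6/120 = 5% of all women, or 6/60 = 10% of one group. With no reversals, power at n = 120 is 3% for 2% conversion, 15% for 3%, 56% for 5% and 98% for 10%.

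All of that conversion must come from women with long-standing symptoms. If 5 to 30% of participants have them below threshold and 10 to 50% of those cross it (both ranges are assumed), conversion is 0.05 × 0.10 = 0.5% to 0.30 × 0.50 = 15%. Power then runs from near 0 to near 100%.

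**The case against.** Several limits on the point are fair, and they stand.

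- A reader might infer that H1 must come out null whatever stimulation does. The documents do not support this. Step 3 shows movement in both directions near the threshold, and Step 4 shows that its size depends on a group whose frequency the protocol does not give.
- A reader might also infer that women with IBS at baseline cannot lose the diagnosis, or that no status changes at all are to be expected among the 120. Neither follows. Part of the recall window is replaced between visits, and items 41 to 43 are percentages that can move either way. The zero applies only to cases arising from new-onset symptoms.
- The overlap figure depends on an unstated baseline date. A gap of three months or more between the two forms would leave no overlap, and a woman whose pain predates baseline could pass the six-month mark by pick-up. That does not help symptoms that begin with stimulation.
- Section 9.3.1 states the onset rule for Rome IV only. For Rome III it follows from the form, because item 40b also uses three months and item 48 is the only onset item. But item 48 asks about pain, and the protocol does not say how it applies to a woman with discomfort only.
- The study is exploratory, and change in IBS-SSS is already part of the primary objective. This limits the harm. It does not repair H1, and the summary still names prevalence alone as the primary endpoint.

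**Conclusion.** The point holds in this form: H1 cannot count Rome IV cases whose symptoms begin during stimulation. That conclusion needs only the onset rule, item 48 and the pick-up timing, and it holds for every course length considered (154 to 174 days short of six months for 8 to 28 days). For Rome III it is an inference from the questionnaire.

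The dilution of 82 to 91% is secondary and rests on the assumed 8 to 16 days with baseline at the start. H1 is insensitive to new-onset symptoms; how close to null it sits overall cannot be determined from the documents. An unchanged Rome prevalence would not show that stimulation causes no IBS-type symptoms.

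**What to change.** Make change in IBS-SSS the primary before/after endpoint in sections 4, 6.1, 6.1.1, 6.3 and 10.5. Use Rome III and Rome IV status at baseline as a descriptor and as an effect modifier for the IBS-SSS change.

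If a before/after Rome comparison is kept, make it secondary and descriptive, and state beside it that it excludes symptoms with onset during treatment. In that case also state how item 48 is scored for a woman who reports discomfort without pain.

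The cost is a protocol amendment, best made before any before/after data are examined. No extra women, visits or forms are needed, and IBS-SSS data already collected remain usable. The study gives up a headline on change in IBS prevalence, and IBS-SSS measures symptom severity, not a diagnosis.

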10.1 Monitoring

The investigator must make all trial documentation and related records available in case a monitoring visit or audit by the Sponsor is requested. Also in case of regulatory inspections all trial documentation should be made available to the inspector(s). All participant data must be handled and treated confidentially.

The Sponsor's monitoring frequency will be determined prior to the start of the trial. A monitoring plan will be generated detailing the frequency and scope of monitoring for the trial. Throughout the course of the trial the monitoring plan can be adjusted as necessary.

10.2 Data Collection

All questionnaires will initially be collected on paper. Each paper questionnaire will be assigned a unique study code and will not contain any identifiable participant information. The linkage between study codes and participant identities will be securely stored and accessible only to the study investigators. Completed paper questionnaires will subsequently be entered into the REDCap system in a timely manner.

An Electronic Data Capture system "**REDCap**" will be used for data collection. The system is validated and access to all levels will be granted/revoked by the Sponsor representative. Trial data should be entered within reasonable time after the subject attended the visit. Corrections/modifications will be automatically tracked by an audit trail detailing date and time of the correction and the name of person performing the correction.

10.3 Data collection from patient file

The patient file will be utilized to collect specific data for the purpose of this study. The following information will be gathered: age, the type of medication administered for ovarian stimulation, the hormonal profile, the number of follicles observed on the final ultrasound, and the number of oocytes retrieved during oocyte pick-up (OPU). This data will be obtained post-OPU.

10.4 Database Management and Quality Control

The investigator should ensure the accuracy, completeness, legibility, and timeliness of the data reported to the sponsor in the eCRF and in all required reports.

The investigator must keep source documents for each subject in the study. All information on the eCRF must be traceable to these source documents, which are generally stored in the subject's medical file. The source documents should contain all demographic and medical information, including laboratory data, ultrasound data, etc., and the original signed informed consent forms. Data reported on the eCRF that derive from source documents should be consistent with the source documents or the discrepancies should be explained.

The investigator and the sponsor should maintain the study documents as specified in the "Essential Documents for the Conduct of a Clinical Trial" chapter 8 of ICH-GCP and as required by the applicable regulatory requirement(s).

These are documents which individually and collectively permit evaluation of a study and the quality of the data produced and include groups of documents, generated before the study

commences, during the clinical study, and after termination of the study and include but are not limited to: study protocol, amendments, submission and approval of EC, raw data of subjects including lab tests, insurance contracts, signed informed consent forms, confidential subjects identification code, eCRF, curricula vitae of the investigator and other participants in the study, study staff lists and responsibilities, monitoring reports and final study report.

The investigator and the sponsor should take measures to prevent accidental or premature destruction of these documents.

The investigator and the sponsor must retain study documents as long as needed to comply with ICH-GCP, national and international regulations. By signing the protocol, the investigator and the sponsor agree to adhere to these requirements.

